## **APPENDIX K: Guidelines for Management of Gastrointestinal Adverse Events**

If GI adverse events are not appropriately managed, they may be associated with the development of dehydration. Management of gastrointestinal adverse events is discussed in detail below.

### **Nausea, vomiting, or both**

In subjects who have emesis and are unable to retain lapatinib, every attempt should be made to obtain control of nausea and vomiting. A dose may be repeated if tablets can be visually found after the vomiting episode.

### **Diarrhea**

These broad general management principles are recommended to proactively try and avoid more serious complications by active management of diarrhea syndrome. Guidelines such as these should never replace sound clinical judgment. Experience thus far suggests that when lapatinib is used as monotherapy, uncomplicated Grade 1 or 2 diarrhea is most prevalent. These general management principles do not address comprehensive management of more serious or protracted diarrhea syndromes.

Common clinical sense with the onset of uncomplicated Grade 1-2 diarrhea: stop all lactose containing products: drink 8-10 large glasses of clear liquids a day; eat frequent small meals; for Grade 2 diarrhea hold cytotoxic chemotherapy, and consider a dose reduction of lapatinib (discuss with Sponsor); administer standard doses of loperamide: initial dose 4 mg followed by 2 mg every 4 hours or after every unformed stool. It is suggested to continue loperamide until the subject is free from diarrhea for 12 hours.

For Grade 3 or 4 diarrhea or Grade 1 or 2 with complicating features (severe cramping, severe nausea/vomiting, decreased performance status, fever, sepsis, Grade 3 or 4 neutropenia, frank bleeding, dehydration) use intravenous fluids as appropriate, consider hospital administration. Use prophylactic antibiotics as needed (example fluoroquinolones) especially if diarrhea is persistent beyond 24 hours or there is a fever or Grade 3-4 neutropenia, hold both cytotoxic chemotherapy and lapatinib and discuss with medical monitor.

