## 5.2 Dosing Delays/Modifications

General guidelines for treatment modifications at the time of re-treatment:

Adverse Events: All adverse events in this trial will be graded using the NCI Common Terminology Criteria for Adverse Events (CTCAE) version 4.0 - a complete listing is available at the CTEP website:  
<http://ctep.cancer.gov/forms/CTCAEv4.pdf>.

Dose adjustments will be made according to the guidelines below, with dose levels defined as follows:

Dose Level (DL)	Agent Dose
0	Lapatinib 500 mg twice daily
-1*	Lapatinib 1000 mg once daily

-2*	Lapatinib 750 mg once daily
-----	-----------------------------

\* The Cmax for lapatinib is higher when administered at a BID dose.

Please refer to Table 2 (background section) for specific values.

**Table 5** Summary of dose holding/interruptions and dose de-escalation recommendations for lapatinib in case of lapatinib-related adverse events (graded according to NCI-CTCAE v4.0)

General Adverse Events	Action
Non-hematological, Grade 1 or 2	Continue lapatinib therapy at full dose prescribed. Apply maximum supportive care recommendations. If prolonged duration of Grade 2 adverse event ( $\geq 7$ days) is affecting quality of life, decrease dose to DL -1, if symptoms persist and continue to affect quality of life for $\geq 7$ more days, a second dose reduction to DL -2 will be allowed.
Non-hematological, Grade 3 or 4 (excluding cardiac and hepatobiliary events)	Apply maximum supportive care recommendations. Hold lapatinib therapy until recovery to Grade $\leq 1$ (up to 14 days). For NCI-CTCAE v4.0 Grade 3 or 4 interstitial pneumonitis or Grade 4 rash manifested as toxic epidermal necrolysis (e.g. Stevens-Johnson Syndrome etc) lapatinib must be permanently discontinued If recurrence of adverse event after drug hold/interruptions is observed, and maximum supportive care measures applied, hold drug once again until recovery to Grade $\leq 1$ (up to 14 days) and restart drug at DL-1. If adverse event recurs, a second dose reduction to DL -2 will be allowed after symptoms recover to Grade $\leq 1$ .
Non-hematological, Grade 3 or 4 adverse events NOT resolved to Grade $\leq 1$ within a maximum of 2 weeks from last planned administration	Action (discontinue or resume lapatinib therapy) in individual cases after discussions with the Sponsor. Up to 2 reductions (DL-1 and DL-2) will be considered after maximum supportive care recommendations are introduced.
Cardiac Adverse Events	

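### Table 5 and Appendix K give different lapatinib actions for part of Grade 1-2 diarrhea, and neither is said to take precedence

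*Combined protocol and SAP*

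**What the plan says.** Table 5 (Section 5.2) sets one action for non-hematological Grade 1 or 2 events: "Continue lapatinib therapy at full dose prescribed. Apply maximum supportive care recommendations". The one exception is a Grade 2 event that has lasted 7 days or more and "is affecting quality of life, decrease dose to DL -1", with a second step down if it persists for 7 further days. In the general non-hematological rows a hold appears only at Grade 3 or 4: "Hold lapatinib therapy until recovery to Grade" 1 or less, for up to 14 days.

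Appendix K (Diarrhea) treats the same event in two paragraphs. For uncomplicated Grade 1-2 diarrhea it gives diet, fluids and loperamide, and adds: "for Grade 2 diarrhea hold cytotoxic chemotherapy, and consider a dose reduction of lapatinib", to be discussed with the sponsor. The next paragraph opens "For Grade 3 or 4 diarrhea or Grade 1 or 2 with complicating features", lists features such as fever, sepsis, bleeding and dehydration, and ends with the instruction to "hold both cytotoxic chemotherapy and lapatinib and discuss with medical monitor".

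Section 5.5 refers sites to Appendix K for gastrointestinal events. No sentence says which text prevails where it differs from Table 5.

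**The concern.** Section 2.2 names diarrhea as the most common adverse event on lapatinib, so a disagreement about its handling is likely to arise in practice. In a multicenter trial, one site could keep a patient at full dose under Table 5 while another holds or reduces under Appendix K for the same presentation.

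Three things follow.

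- **Safety.** The sharper disagreement concerns patients with features such as fever or dehydration, where consistent handling matters most.
- **Deviations.** Section 7.6.1 requires all deviations to be reported to the NCI-IRB. For complicated Grade 1-2 diarrhea, holding departs from Table 5 and continuing departs from Appendix K, so it is unclear what counts as a deviation.
- **Drug exposure.** Days on hold count toward the Section 5.2 limit of 21 days without drug in any 90. Under Section 12.5.2, patients with an incorrect schedule stay in the response analysis. Differences in dosing between sites would therefore remain in the analyzed data.

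**Working it through.** **The texts side by side**

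| Diarrhea | Table 5, Section 5.2 | Appendix K | Relation |
|---|---|---|---|
| Grade 1, uncomplicated | Full dose, supportive care | Diet, fluids, loperamide; no lapatinib change | Agree |
| Grade 2, uncomplicated | Full dose; reduce only after at least 7 days with quality-of-life impact | Consider reducing at onset, with the sponsor; no duration or quality-of-life condition | Differ in timing and conditions |
| Grade 1-2 with complicating features that do not reach Grade 3-4 | Full dose, with the same Grade 2 exception | Hold; discuss with the medical monitor | Opposed |
| Grade 3-4 | Hold | Hold; discuss with the medical monitor | Agree on holding |

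The Appendix K hold sentence is loosely punctuated. It can be read as covering everything in its paragraph, or only diarrhea persisting beyond 24 hours, fever, or Grade 3-4 neutropenia. Under either reading some Grade 1-2 diarrhea is held in Appendix K and continued in Table 5.

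The Grade 2 timing difference has practical weight. Section 2.2 (GI Toxicity) gives a median diarrhea duration of 5 days. An episode of that length cannot meet Table 5's 7-day condition, but if Grade 2 it falls under Appendix K's prompt from the start. The 5-day figure is not specific to Grade 2.

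**How many patients**

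Inputs: Table 3 (Section 2.2), Grade 1-2 drug-related diarrhea; 25 evaluable patients (Section 12.1).

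1. Table 3's own figures reproduce: 22/69 = 31.9% (printed 32) at 500 mg twice daily, and 45/138 = 32.6% (printed 33) overall.
2. Expected number with any Grade 1-2 diarrhea: 25 × 22/69 = 7.97, about 8. The exact 95% interval for 22/69 is 21.2% to 44.2%, which gives 25 × 0.212 = 5.3 to 25 × 0.442 = 11.1 patients.
3. This counts every Grade 1-2 case, including uncomplicated Grade 1, where the texts agree. The documents neither split Grade 1 from Grade 2 nor report complicated cases, so the disputed share s has to be assumed. The expected number is 25 × (22/69) × s, and the chance of at least one is 1 − (1 − (22/69) × s)^25.

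| Assumed s | Rate | Expected in 25 | Chance of at least one |
|---|---|---|---|
| 10% | 3.2% | 0.8 | 0.56 |
| 25% | 8.0% | 2.0 | 0.88 |
| 50% | 15.9% | 4.0 | 0.99 |
| 75% | 23.9% | 6.0 | above 0.99 |
| 100% (ceiling) | 31.9% | 8.0 | above 0.99 |

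**The case against.** The strongest reply is that the plan shows which text governs dosing. Section 5.1 points to Section 5.2 for modifications, and Section 5.2 says adjustments follow its own guidelines. Appendix K is cited under supportive care and says of itself: "Guidelines such as these should never replace sound clinical judgment". This carries weight, and many investigators would read it that way. It is an inference from placement, however. Appendix K contains explicit lapatinib instructions, and deference to clinical judgment does not settle hold against continue.

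Several limits on the point stand in full.

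- A reader might infer that the texts conflict for all Grade 1-2 diarrhea. They do not: uncomplicated Grade 1 agrees.
- The word hold in the Grade 2 sentence concerns chemotherapy, not lapatinib. For lapatinib that sentence says only to consider a reduction, which Table 5 also permits later.
- A complicating feature that is itself a Grade 3 or 4 non-hematological event already brings Table 5's hold into play, whatever the diarrhea grade. The opposition is therefore confined to lesser features, such as a low-grade fever.
- Section 2.2 reports that 85% of patients needed no dose adjustment or interruption for diarrhea, and that none in the phase 1 500 mg twice-daily group needed a reduction. Those figures suggest few dose actions, although they reflect the rules of those earlier studies.

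A reader might also infer from the chemotherapy wording that Appendix K was written for combination regimens. The documents do not show this: the appendix speaks of monotherapy as well as combinations. They show only that those clauses have no application here, because Sections 5.1 and 5.5 exclude other anti-tumor treatment.

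**Conclusion.** The point holds in a narrow form. Table 5 and Appendix K are opposed for Grade 1-2 diarrhea with complicating features below Grade 3. They differ in timing and conditions for uncomplicated Grade 2. No explicit rule of precedence resolves either.

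A reader might take 8 of 25 as the number affected. It is a ceiling: it applies the rate of all Grade 1-2 diarrhea to a smaller group. Under an assumed disputed share of 25% to 75%, about 2 to 6 of 25 patients are affected; at 10% it is fewer than one. These figures also assume that a breast cancer rate carries over to melanoma. Section 2.2 itself quotes two all-grade diarrhea figures, 36% and 46%.

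A reader might further infer a bias in the response rate. The documents give no basis for its direction or size. Sample size, error rates and the two-stage decision rule are unaffected. This is a minor inconsistency of wording, worth correcting for consistent safety handling across sites.

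**What to change.** Reconcile the Table 5 row for non-hematological Grade 1 or 2 events with the diarrhea text in Appendix K. Each grade, with and without complicating features, should have one stated lapatinib action; alternatively, an explicit sentence should say which text takes precedence. Punctuate the Appendix K hold sentence so that its trigger is unambiguous. Remove the instructions about cytotoxic chemotherapy, which do not apply to this monotherapy trial. The clinical team must decide what the action is; this review takes no view.

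The cost is amendment wording in one appendix and one table row, with no change to sample size or analysis.

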### **Treatment of gastrointestinal adverse events**

Diarrhea can be debilitating, and on rare occasions, it is potentially life-threatening. Based on experience with lapatinib alone or in combination with taxanes and/or trastuzumab, diarrhea should be managed proactively to avoid complications or worsening of the patient's condition. Guidelines developed by an American Society of Clinical Oncology (ASCO) panel for treating chemotherapy-induced diarrhea are abstracted below.

Pharmacological approaches include the following:

Loperamide, administered as an initial 4-mg dose, followed by 2-mg doses every

4 hours. This dose and regimen are moderately effective.

Clonidine, non-steroidal anti-inflammatory drugs, and the serotonin antagonist cyproheptadine have been shown to be effective in controlling diarrhea associated with inflammation of the bowel.

The synthetic octapeptide, octreotide, has been shown to be effective in the control of diarrhea induced by fluoropyrimidine-based chemotherapy regimens when administered as an escalating dose by continuous infusion or subcutaneous injection. Octreotide can be administered at doses ranging from 100  $\mu\text{g}$  twice daily to 500  $\mu\text{g}$  3 times daily, with a maximum-tolerated dose of 2000  $\mu\text{g}$  3 times daily in a 5-day regimen.

## APPENDIX L: CTEP MULTICENTER GUIDELINES

If an institution wishes to collaborate with other participating institutions in performing a CTEP sponsored research protocol, then the following guidelines must be followed.

### Responsibility of the Protocol Chair

- The Protocol Chair will be the single liaison with the CTEP Protocol and Information Office (PIO). The Protocol Chair is responsible for the coordination, development, submission, and approval of the protocol as well as its subsequent amendments. The protocol must not be rewritten or modified by anyone other than the Protocol Chair. There will be only one version of the protocol, and each participating institution will use that document. The Protocol Chair is responsible for assuring that all participating institutions are using the correct version of the protocol.
- The Protocol Chair is responsible for the overall conduct of the study at all participating institutions and for monitoring its progress. All reporting requirements to CTEP are the responsibility of the Protocol Chair.
- The Protocol Chair is responsible for the timely review of Adverse Events (AE) to assure safety of the patients.
- The Protocol Chair will be responsible for the review of and timely submission of data for study analysis.

### Responsibilities of the Coordinating Center

- Each participating institution will have an appropriate assurance on file with the Office for Human Research Protection (OHRP), NIH. The Coordinating Center is responsible for assuring that each participating institution has an OHRP assurance and must maintain copies of IRB approvals from each participating site.
- Prior to the activation of the protocol at each participating institution, an OHRP form 310 (documentation of IRB approval) must be submitted to the CTEP PIO.
- The Coordinating Center is responsible for central patient registration. The Coordinating Center is responsible for assuring that IRB approval has been obtained at each participating site prior to the first patient registration from that site.
- The Coordinating Center is responsible for the preparation of all submitted data for review by the Protocol Chair.
- The Coordinating Center will maintain documentation of AE reports. There are two options for AE reporting: (1) participating institutions may report directly to CTEP with a copy to the Coordinating Center, or (2) participating institutions report to the Coordinating Center who in turn report to CTEP. The Coordinating Center will submit AE reports to the Protocol Chair for timely review.
- Audits may be accomplished in one of two ways: (1) source documents and research records for selected patients are brought from participating sites to the Coordinating Center for audit, or (2) selected patient records may be audited on-site at participating sites. If the NCI chooses to have an audit at the Coordinating Center, then the Coordinating Center is responsible for having all source documents, research records, all IRB approval documents, NCI Drug Accountability Record forms, patient registration

lists, response assessments scans, x-rays, etc. available for the audit.

#### Inclusion of Multicenter Guidelines in the Protocol

- The protocol must include the following minimum information:
  - The title page must include the name and address of each participating institution and the name, telephone number and e-mail address of the responsible investigator at each participating institution.
  - The Coordinating Center must be designated on the title page.
  - Central registration of patients is required. The procedures for registration must be stated in the protocol.
  - Data collection forms should be of a common format. Sample forms should be submitted with the protocol. The frequency and timing of data submission forms to the Coordinating Center should be stated.
  - Describe how AEs will be reported from the participating institutions, either directly to CTEP or through the Coordinating Center.
  - Describe how Safety Reports and Action Letters from CTEP will be distributed to participating institutions.

#### Agent Ordering

- Except in very unusual circumstances, each participating institution will order DCTD-supplied agents directly from CTEP. Agents may be ordered by a participating site only after the initial IRB approval for the site has been forwarded by the Coordinating Center to the CTEP PIO.
